7.3.6. Effectiveness evaluation

(1) Clinical response

The clinical response of this drug should be evaluated comprehensively at the completion of the observation period, and the results should be recorded.

If this drug is administered continuously for more than 8 weeks, the clinical response should be evaluated comprehensively at Week 8.

- Effective
- Not effective
- Indeterminate (the reason should be recorded.)

The assessment criteria shall be as follows:

Table 2. Assessment criteria for [anaerobic infection] / [infectious enterocolitis (including pseudomembranous colitis)]

Assessment	Definition
Effective	Clinical symptoms accompanying the infection observed at the initiation of treatment with this drug has improved at the time of assessment, and treatment with other antibacterial drugs after the time of assessment is determined not necessary.
Not effective	"Effective" criteria are not met.
Indeterminate	Clinical response is difficult to evaluate.

Table 3. Assessment criteria for [amebic dysentery]

Assessment	Definition
Effective	Clinical symptoms accompanying the infection observed at the initiation of treatment with this drug has improved at the time of assessment, and treatment with other antibacterial drugs other than antiamebic agents (paromomycin, etc.) after the time of assessment is determined not necessary.
Not effective	"Effective" criteria are not met.
Indeterminate	Clinical response is difficult to evaluate.

Any clinically problematic finding compared to the initiation of treatment should be recorded in details in the AE column.

(2) Rationale for clinical response assessment

The rationale for the clinical response assessment ("Effective" or "Not effective"), on the disease for which this drug is used, should be recorded.

[Anaerobic infection]

General clinical findings, body temperature, WBC count, CRP level, imaging, and others

[Infectious enterocolitis (including pseudomembranous colitis)]

General clinical findings, Clostridium difficile TOXIN test, frequency of diarrhea, body temperature, abdominal pain, and others

[Amebic dysentery]

General clinical findings, ameba test, frequency of diarrhea, body temperature, abdominal pain, and others

(3) Microbiological response assessment

Microbiological response at the completion of observation period compared to prior to the initiation of treatment with this drug should be assessed, and the results should be recorded.

Table 4. Assessment criteria for microbiological response

Assessment	Definition
Eradication	Pathogen is not detected in the specimen appropriately collected following administration of this drug.
Presumed eradication	Pathogen is presumed eradicated if the treatment improves or resolves the clinical symptoms, and a specimen suitable for the test is no longer available in the original infection focus.
Partial eradication	Pathogen is partially detected in the specimen appropriately collected following administration of this drug.
Persistence	No improvement of clinical symptoms is confirmed, and the pathogen is detected in the infection focus.
Indeterminate	A microbiological test was conducted, but no pathogen could be isolated or estimated. Or a microbiological test was not conducted due to various reasons.

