7.7. Data analysis

The details of methods of analysis on data collected in this study shall be described in the statistical analysis plan (SAP) to be separately prepared.

- Definition of analysis set

The safety analysis set shall include patients for whom the registration in this study and administration of this drug have been confirmed.

Two analysis sets, which are clinically-evaluable analysis set and microbiological analysis set shall be defined as the effectiveness analysis set. The clinically-evaluable analysis set includes patients who were confirmed to conduct the clinical evaluation in the safety analysis set. The microbiological analysis set includes patients for whom microbiological response was assessed in the clinically-evaluable analysis set.

- Methods of analysis

(1) Analysis for safety evaluation

The incidence of adverse reactions will be calculated for each event. Also, the factors affecting the occurrence of adverse reaction will be evaluated as necessary.

(2) Analysis for effectiveness evaluation

The clinical response rate in terms of the clinical effectiveness will be set as the primary effectiveness endpoint. The number of patients with "effective" and its proportion (clinical response rate) among the clinically-evaluable analysis set, and its 95% confidence interval will be calculated. The number of patients with eradication or presumed eradication, and its proportion (eradication rate) among the microbiological analysis set, and its 95% confidence interval will be calculated. The clinical response rate for each disease and its 95% confidence interval, and the eradication rate and its 95% confidence interval will be calculated. Also, an exploratory analysis on the factors affecting the effectiveness will be performed as necessary.

$$\text{Clinical response rate (\%)} = \frac{\text{Number of patients with "effective"} }{\text{Number of clinically-evaluable patients excluding "indeterminate"} } \times 100$$

$$\text{Eradication rate (\%)} = \frac{\text{Number of patients with "eradication" + "presumed eradication"} }{\text{Number of patients in the microbiological analysis set excluding "indeterminate"} } \times 100$$

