6.2.2. Microbiological Response

At the end of observation period or at the time of discontinuation, microbiological response will be assessed by the physician according to the criteria below. If this drug is administered continuously for more than 8 weeks, the clinical response should be evaluated comprehensively at Week 8.

- Eradication: Pathogen is not detected in the specimen appropriately collected following administration of this drug.
- Presumed eradication: Pathogen is presumed eradicated if the treatment improves or resolves the clinical symptoms, and a specimen suitable for the test is no longer available in the original infection focus.
- Partial eradication: Pathogen is partially detected in the specimen appropriately collected following administration of this drug.
- Persistence: No improvement of clinical symptoms is confirmed, and the pathogen is detected in the infection focus.

- Indeterminate: A microbiological test was conducted, but no pathogen could be isolated or estimated. Or a microbiological test was not conducted due to various reasons.

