7. HANDLING OF MISSING DATA

When the seriousness/outcome of adverse events and action taken with Anametro for the adverse events are missing, these data are handled as “unknown” for counting.

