8.2.4.2. Microbiological Response

In the microbiological response analysis set, the number and proportion of patients with each microbiological response will be calculated. In addition, the number and proportion (eradication rate) of patients who fall in “eradication” or “presumed eradication” categories

and the 95% CI of eradication rate will be calculated in the microbiological response analysis set excluding patients with indeterminate response. Similar calculations will be tabulated by diagnosis (including by detailed diagnostic name of anaerobic infection), by maximum number of daily doses, and by the occurrence of central nervous system disorder. The eradication rate can be calculated by the following formula:

Eradication rate (%) = (Number of patients with “eradication” plus “presumed eradication”/ Number of patients in the microbiological analysis set excluding “indeterminate”) × 100.

In addition, the number and proportion (eradication rate) of patients who fall in “eradication” or “presumed eradication” categories and the 95% CI of eradication rate for each pathogenic organism/strain will also be tabulated by diagnosis.

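### The eradication rate infers the microbiological result from the clinical course in one direction only, so it is probably biased upward

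*Protocol*

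**What the plan says.** Table 4 in protocol 7.3.6 defines five microbiological outcomes, and SAP 6.2.2 repeats them unchanged. Three matter here.

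- *Presumed eradication*, judged at the original site, has this definition: "Pathogen is presumed eradicated if the treatment improves or resolves the clinical symptoms, and a specimen suitable for the test is no longer available".
- *Persistence*: "No improvement of clinical symptoms is confirmed, and the pathogen is detected in the infection focus". Partial eradication likewise requires a collected specimen in which the pathogen is found.
- *Indeterminate*: a test was done but yielded no pathogen, or, as the second limb puts it, "Or a microbiological test was not conducted due to various reasons".

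Protocol 7.7 puts presumed eradication in the numerator: "The number of patients with eradication or presumed eradication, and its proportion (eradication rate) among the microbiological analysis set". Its formula removes 'Indeterminate' patients from the denominator. SAP 8.2.4.2 does the same: the rate and its interval "will be calculated in the microbiological response analysis set excluding patients with indeterminate response". The interval is exact (SAP 8.1.3).

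SAP section 7, on missing data, is confined to adverse-event fields ("When the seriousness/outcome of adverse events and action taken with Anametro for the adverse events are missing"). No sensitivity analysis for 'Indeterminate' microbiology is planned.

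**The concern.** This is a chart-based study, and protocol 7.9 itself warns that planned data may be missing, so absent post-treatment specimens are foreseeable. When one is absent, the clinical course stands in for the laboratory result if the patient improved. It does not if the patient failed to improve, because there is no 'presumed persistence' category to mirror 'presumed eradication'. The unimproved patient is not scored as a failure but drops out.

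What is at stake is the planned microbiological effectiveness measure and its confidence interval. The final analysis supports the re-examination application (SAP 3). A reader would take the rate as the share of evaluable patients in whom the pathogen was cleared, when part of that share may come from removing likely failures.

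**Working it through.** **Plan's own figures.** The documents give no expected eradication rate, retest rate or specimen availability, so there is nothing to reproduce on this point. The one design figure, 95% probability of seeing a 3% reaction in 100 patients, does reproduce (1 − 0.97^100 = 0.952), but it is not an input here.

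**Step 1: put each kind of patient through the rule.**

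| Clinical course | Post-treatment microbiology | Category | Numerator | Denominator |
|---|---|---|---|---|
| Improved | Specimen, pathogen absent | Eradication | yes | yes |
| Improved | No suitable specimen left | Presumed eradication | yes | yes |
| Improved | Test simply not done | Indeterminate | no | no |
| Not improved | Specimen, pathogen found | Persistence | no | yes |
| Not improved | No test | Indeterminate | no | no |

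The last row follows by elimination. Persistence and partial eradication both need a detected pathogen, and presumed eradication needs improvement. The documents do not name this case.

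**Step 2: illustrate the size.** All inputs are assumptions: 100 patients with a baseline pathogen; 40 retested, of whom 75% (30) are eradicated; 60 untested, of whom 80% (48) improved and 12 did not; no specimen obtainable in any untested patient. Intervals are exact 95%.

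- Planned rate: (30 + 48)/(40 + 48) = 78/88 = 88.6% (80.1 to 94.4).
- The 12 kept as not eradicated: 78/100 = 78.0% (68.6 to 85.7).
- Documented results only: 30/40 = 75.0% (58.8 to 87.3).

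**Step 3: vary the retested number**, other inputs fixed.

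| Retested | Planned rate | Unimproved untested kept | Gap (points) |
|---|---|---|---|
| 20 | 79/84 = 94.0% | 79.0% | 15.0 |
| 40 | 78/88 = 88.6% | 78.0% | 10.6 |
| 60 | 77/92 = 83.7% | 77.0% | 6.7 |
| 80 | 76/96 = 79.2% | 76.0% | 3.2 |

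**Step 4: vary the unimproved share of the untested.** With 40 retested and only 5% of the 60 untested unimproved (3 patients), 57 are presumed eradicated. The planned rate is (30 + 57)/(40 + 57) = 87/97 = 89.7%, against 87/100 = 87.0%: a gap of 2.7 points.

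**Step 5: let x of the 48 improved untested patients be 'Indeterminate'** because a test was simply omitted. The planned rate is (78 − x)/(88 − x).

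- x = 24: 54/64 = 84.4%.
- x = 48: 30/40 = 75.0%, below the 78.0% comparator.
- Break-even with 78.0%: 78 − x = 0.78(88 − x), so x = 9.36/0.22 = 42.5, about 89% of the 48.

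Break-even depends on the inputs. With 80 improved and 20 unimproved patients, all 80 eradicated and none of the 20, and half of the 20 'Indeterminate', the planned rate is 80/90 = 88.9% against a true 80%. The excess is gone when half of the improved are also 'Indeterminate' (40/50 = 80.0%) and reverses at 60% (32/42 = 76.2%).

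**The case against.** The strongest objection is that 'Indeterminate' is not reserved for unimproved patients. Presumed eradication requires that no suitable specimen remains. An improved patient from whom a specimen could have been taken, but was not, is 'Indeterminate' too, and that pulls the rate down. Step 5 shows this can offset the upward pull. This stands: it limits the conclusion to a probable direction of unknown size.

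For the same reason, two tempting inferences go too far. A reader might conclude that the rate rises whenever fewer patients are retested, whatever the drug does, and would reach 100% if nobody were retested. That holds only if every untested improved patient had no obtainable specimen; if tests were simply omitted in everyone, the rate would be 0/0. A reader might also take the 3 to 15 points of Step 3 as the size of the bias. That range varies the retested number alone. If specimens become unavailable as patients recover, unimproved patients are the ones more likely to have been tested, which favours the smaller gap of Step 4.

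Second, SAP 8.2.4.2 already tabulates the number in each category, and SAP 9 lists clinical and microbiological response by patient. The presumed-only and 'Indeterminate' counts will therefore be visible. This stands, but the rate and interval that will be quoted still exclude the unimproved untested patients, and no alternative is pre-specified.

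Third, clinical response is the primary effectiveness endpoint (protocol 7.7), the study is not confirmatory and has no decision rule (SAP 4.1, 4.2), and the comparison with the earlier clinical study in protocol 7.5.2 concerns clinical response. This stands and bears on priority.

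The organism-level rule in SAP 6.2.3 offers no correction. It counts an organism as eradicated when no specimen could be collected, without requiring clinical improvement.

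**Conclusion.** The one-sided inference is in the current text of both documents, and nothing else in them removes it. The eradication rate is probably biased upward. Under the assumptions of Step 2 the planned rate is 88.6% against 78.0%. The gap falls to 2.7 points if 5% rather than 20% of the untested are unimproved, and it can vanish or reverse if many improved patients are 'Indeterminate' because a test was omitted. The documents support neither a certain direction nor a particular size. Priority is moderate: a secondary, descriptive measure, but one with a cheap correction.

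**What to change.** In SAP 8.2.4.2, keep the physician's categories and the planned rate, and add two pre-specified rates with exact 95% intervals.

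1. **Rate with presumed persistence.** Patients assessed as 'Indeterminate' who had a pathogen recorded before treatment, no post-treatment microbiological test and clinical response 'Not effective' stay in the denominator as not eradicated. The rule must be limited to 'Indeterminate' patients. 'Not effective' includes improved patients who still needed other antibacterial drugs, and some of these properly meet presumed eradication; they must not be reclassified.
2. **Documented rate.** Eradication / (eradication + partial eradication + persistence).

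The presumed-only count is already in the planned category table.

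The cost is SAP wording and one derived variable. Pathogen, test and clinical response data are already collected (protocol 7.3.4.2 and 7.3.6). The downside is that the first added rate is less favourable and somewhat conservative, because of the breadth of 'Not effective'. It also leaves out improved patients who are 'Indeterminate': with x = 24 in Step 5 it would be 54/76 = 71.1%. It should be read beside the planned rate as a lower reading, with the number of 'Indeterminate' patients whose clinical response was 'Effective' stated.

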7.3.7. Adverse events

After confirming the occurrence of AEs from the initiation of treatment with this drug to the completion date of observation period, the following information will be recorded. Upon occurrence of any AE, the investigator should take appropriate measures, and promptly report to Pfizer Japan Inc. (hereinafter "Sponsor"), and if causal relationship with this drug cannot be ruled out, the investigator should follow up the event until the AE or its sequelae are resolved or stabilized at the level acceptable to the investigator and Sponsor.

Moreover, a study should be separately conducted in detail on patients in whom a serious adverse reaction, or an adverse reaction not described in the package insert occurred if it is determined necessary by Sponsor.

[1] Presence/absence of AE

[2] Name of AE

[3] Presence/absence of AE concerning central nervous system disorder

[4] Date of occurrence

[5] Intervention

[6] Seriousness

[7] Outcome

[8] Causal relationship

[If the AE is associated with abnormal change in laboratory values, i.e., clinical laboratory tests, the following information should also be recorded.]

[1] Laboratory parameter

[2] Site reference value

[3] Unit

[4] Date measured

[5] Results

Detailed study on adverse reactions concerning central nervous system disorder

Completion of detailed CRF should be separately requested on central nervous system disorder that occurred in patients subject to this study if it is determined necessary by Sponsor.

7.3.8. Major investigation items

N/A

7.4. Data sources

In this study, the investigator extracts the necessary information from the medical record in accordance with the protocol.

7.5. Study size

7.5.1. Planned sample size

100 patients (for safety analysis)

7.5.2. Rationale for sample size

The target sample size was set to be 100 patients, which should enable to detect, at 95% probability, an adverse reaction of which the true incidence rate is 3% in reference to adverse reaction of the least incidence in a clinical study of this drug (Study A6831005). This sample size should enable to confirm whether the types and incidence of adverse reaction related to this

drug used for diseases other than intra-abdominal infection, and pelvic inflammatory disease and other related diseases (hereinafter referred to as "PID") that were targeted in the clinical study would be similar to those occurred in Study A6831005.

Events specified as important identified risks or important potential risks in the Risk Management Plan (RMP) may not have a high incidence, and thus, may not detect sufficient information only from the drug use investigation; nonetheless, such an event collected in the drug use investigation should be investigated within the framework of the drug use investigation. Moreover, these events should also be monitored through the routine pharmacovigilance activities.

The sample size of 100 patients are expected to enable accumulating data on the number of patients at the level similar to the clinical study in terms of clinical response rate of this drug for diseases other than intra-abdominal infection and PID that were targeted in the clinical study and also in terms of clinical response rate in subgroup analysis by each major indication; which should enable verification whether the effectiveness under actual clinical settings is similar to the results of the clinical study.

7.6. Data management

7.6.1. Data collection method

The data for this study will be collected using a specific CRF provided by Sponsor. The investigator will complete the CRFs promptly after the completion of observation period and submit them to the Sponsor.

7.6.2. Patient registration

7.6.2.1. Procedure of patient registration

(1) Registration

The following registration items should be completed in the registration forms for patients with anaerobic infection, infectious enterocolitis, or amebic dysentery who are given Anaemetron I.V. Infusion 500 mg and meet the registration requirements; patients should be registered via FAX at the registration center until the target number of patients is registered. The patients should be registered before Day 8 of treatment counting from the initiation of treatment with Anaemetron I.V. Infusion 500 mg as Day 1.

1) Registration criteria

Patients who have not used Anaemetron I.V. Infusion 500 mg before the initiation of treatment with this drug

2) Registration items

Patient ID number, sex, age on the date of treatment initiation, date of treatment initiation with this drug, eligibility to registration criteria, and disease targeted in this study (disease for which this drug is used)

[Patient Registration Center]

[contact] (Available 24 hours a day)

(2) Exclusion from the registration

Patients found to not meet the registration criteria after the registration form is received at the registration center will be excluded from the registration.

7.6.3. Reminders concerning completion, revision, and submission of case report form

7.6.3.1. Completion

The investigator shall, upon confirming the study items, complete the CRF based on medical charts and other medical records such as relevant test results, using a pen, ballpoint pen, or other inerasable means.

7.6.3.2. Revision

Upon receiving Sponsor's inquiry on the contents of the CRF (query forms), the investigator will again confirm the contents of medical records described earlier, and as required, correct relevant sections and resubmit the form. Corrections in the CRF should be struck out with a double line (=) with a "correction seal" on the double line; the double line should be drawn so that the original contents prior to correction are legible.

7.6.3.3. Submission

CRFs should be submitted promptly upon completion in accordance with the procedures set out by Sponsor.

7.7. Data analysis

The details of methods of analysis on data collected in this study shall be described in the statistical analysis plan (SAP) to be separately prepared.

- Definition of analysis set

The safety analysis set shall include patients for whom the registration in this study and administration of this drug have been confirmed.

Two analysis sets, which are clinically-evaluable analysis set and microbiological analysis set shall be defined as the effectiveness analysis set. The clinically-evaluable analysis set includes patients who were confirmed to conduct the clinical evaluation in the safety analysis set. The microbiological analysis set includes patients for whom microbiological response was assessed in the clinically-evaluable analysis set.

- Methods of analysis

(1) Analysis for safety evaluation

The incidence of adverse reactions will be calculated for each event. Also, the factors affecting the occurrence of adverse reaction will be evaluated as necessary.

(2) Analysis for effectiveness evaluation

The clinical response rate in terms of the clinical effectiveness will be set as the primary effectiveness endpoint. The number of patients with "effective" and its proportion (clinical response rate) among the clinically-evaluable analysis set, and its 95% confidence interval will be calculated. The number of patients with eradication or presumed eradication, and its proportion (eradication rate) among the microbiological analysis set, and its 95% confidence interval will be calculated. The clinical response rate for each disease and its 95% confidence interval, and the eradication rate and its 95% confidence interval will be calculated. Also, an exploratory analysis on the factors affecting the effectiveness will be performed as necessary.

$$\text{Clinical response rate (\%)} = \frac{\text{Number of patients with "effective"} }{\text{Number of clinically-evaluable patients excluding "indeterminate"} } \times 100$$

$$\text{Eradication rate (\%)} = \frac{\text{Number of patients with "eradication" + "presumed eradication"} }{\text{Number of patients in the microbiological analysis set excluding "indeterminate"} } \times 100$$

Detailed methodology for summary and statistical analyses of data collected in this study will be documented in a SAP, which will be dated, filed and maintained by the Sponsor. The SAP may modify the plans outlined in the protocol; any major modifications of primary endpoint definitions or their analyses would be reflected in a protocol amendment.

